3.2 During the study
The following variables (respiratory rate, heart rate, BP, O₂ sat, FIO₂, Dyspnea Borg score, cough, respiratory accessory muscle, peak flow and FEV1) will be recorded at the following time points after initial bronchodilator therapy (30±10 minutes, 60±10 minutes, 180±10 minutes and at the disposition from the ER). If the patient is discharged from the ER within 3 hours from the initial bronchodilator therapy then the data collection at 3 hours mark will be waived.

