For a power calculation to determine the sample size, historical data was utilized from prior clinical study that examined the effect of bronchodilator (B2-agonist) treatment on the improvement of the peak flow measurement after 30 minutes of the initial bronchodilator treatment⁴. In this study, the mean PEFR improved from 27% to 39% at 30 minutes after the initial bronchodilator treatment. We hypothesize that mean PEFR of the intervention group at 30 minutes of the bronchodilator therapy will be at least 10 points higher than the control group (i.e. mean PEFR \geq 49% at 30 minutes of the initial bronchodilator therapy). Group sample sizes of 34 and 34 is required to achieve a power $> 80\%$ to reject the null hypothesis of equal means when the groups mean difference is 10.0 with a standard deviation for both groups of 14.4 and with a significance level (alpha) of 0.050 using a two-sided two-sample equal-variance t-test.

Taking into consideration the screen failures the disqualification and drop-outs, we are anticipating enrolling around 110 patients in order to have 68 patients who will complete the study objectives.

For the statistical analysis treatment evaluations will be performed on the principle of intention to treat (ITT) using the data collected from all randomized participants who completed the study procedures including the two parts of the informed consent form (ICF). Demographics and baseline characteristics of patients will be summarized for each group. Continuous variables will be reported as mean \pm standard deviation, with minimum, median, and maximum values.

Categorical variables will be reported as n and %. All statistical testing will be two-sided with alpha=0.05.

For the primary outcome, mean PEFR at 30 minutes post-bronchodilator treatment, analysis of covariance (ANCOVA) with adjustment for baseline PEFR will be utilized.

ANCOVAs with adjustment for baseline values, and incorporating repeated measures where appropriate, will be utilized for the following secondary outcomes: absolute value of PEFR (L/Min) at 30 minutes, PEFR percentage of predicted at 60 minutes and 180 minutes, FEV1 percentage of predicted as well as absolute FEV1 (L/Sec) at 30 minutes, 60 minutes and 180 minutes, Borg dyspnea score at 30 minutes, 60 minutes and 180 minutes, accessory muscle use score at 30 minutes, 60 minutes and 180 minutes, and heart rate at 30 minutes, 60 minutes and 180 minutes.

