The outcomes which are measured at different time points will be averaged for each group and plotted to visualize the trajectory of those outcomes.

Differences in length of stay (hours) in the ER and the total doses of albuterol and ipratropium will be compared using T-tests or non-parametric methods (e.g., Mann-Whitney test) as depending on the distribution of the data. The proportion of patients in each group who require hospitalization will be compared using a Chi-square test.

C. Subject Characteristics

1. Subject criteria:

The study will be conducted at the emergency department at Tufts Medical Center.

a) Inclusion criteria:

- Acute asthma exacerbations presenting to the emergency room
- Peak expiratory flow rate at presentation <50%40% of predicted
- Enrolment within 90 minutes of the arrival to the ER
- Age 18-55 years old

b) Exclusion criteria:

- History of chronic obstructive pulmonary disease
- Clinical evidence to suggest a non-asthmatic cause of bronchospasm as determined by the treating physician
- Clinical evidence of acute coronary syndrome
- Respiratory failure requiring mechanical ventilation either invasive or non-invasive
- Tachyarrhythmia other than sinus
- Agitated or uncooperative
- Inability to provide informed consent

c) Withdrawal/Termination criteria:

The subject will be withdrawn from the study if any of the following:

- The subject develops respiratory failure requiring mechanical ventilation (invasive or non-invasive)
- The subject becomes unable to perform peak flow measurement at the pre-specified time points
- The treating physician determines that it is not clinically advisable to continue with the study.
- The subject opts to decline to sign the second part of the informed consent form. In this case, the data collected may not be used for the study.

A study participant will have the right to withdraw from the study at any point of the study.

A study participant may not participate in another research study while participating in this study.

D. Risk/benefit assessment:

1. Physical risk:

Patients in both the intervention and control arms are at risk for developing respiratory failure as a result of severe asthma exacerbation and it is unknown if the risk of such complications is higher in any arm. It is possible that the Aeroneb group patient may experience more frequent side effects related to potentially more albuterol and ipratropium delivery and those side effects may include tremor and arrhythmias.

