In order to blind the treating physician and the recording investigator, a sign "treatment in progress" will be displayed at the outdoor of the ER room when the patient is getting the bronchodilator treatment. The nebulizer devices will be placed in the box between the bronchodilator treatment sessions. The physician and the recording investigator will be asked if possible to see the patients only when the sign is taken off the outdoor.

-Once assigned, all the bronchodilator treatments in the ER will be administered using the nebulizer device assigned to that patient.

-The Peak flow and FEV1 will be measured using Spirometer (micro I). Both values will be obtained through the same exhalation maneuver.

-Patient will be treated and managed according to the asthma ER adult protocol or as directed by the ER physician who is in charge of patient's care

-After the study procedures have been performed and the subject is determined to be in stable condition and have the capacity to make medical decisions, the investigator will approach the subject again and review all the elements of the ICF again with the subject. The collected data will be used only if the subject signs both parts of the informed consent.

-Within two weeks of the subject participation, the research team will attempt to conduct a phone interview with the subject to obtain their feedback on the study procedures and mainly on the informed consent process. The phone interview questionnaire is included in the supplement

-The research team will report to the IRB the progress of the study including the consent process after enrolling the first 10 patients.

3. Subject Timeline:

During the study several data will be recorded, most of them are standard hospital recording, which are conducted frequently. These data will be collected at baseline and at multiple points after the initial bronchodilator therapy (at 30 ± 10 minutes, 60 ± 10 minutes, at 180 ± 10 minutes and upon disposition from the ER). All recorded data are obtained through noninvasive measurements. No samples of any body component will be taken that is not part of the normal standard hospital protocols.

The results that will be collected are summarized in table 1.

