Respiratory accessory muscle use		•
Peak flow (percentage from predicted)	•	
Peak flow (L/Min)	•	
FEV1 (percent of predicted)		•
FEV1 (Liter)		•
At (180±10) minutes after nebulizer treatment		
Respiratory rate	•	
Heart rate	•	
Systolic/diastolic blood pressure	•	
O2 sat	•	
FIO2	•	
Dyspnea score		•
Cough		•
Respiratory accessory muscle use		•
Peak flow (percentage from predicted)	•	
Peak flow (L/Min)	•	
FEV1 (percent of predicted)		•
FEV1 (Liter)		•
Upon disposition from the ER		
Disposition (Home, floor or ICU)		•
Length of stay in the ER (from ER arrival time to disposition order placement time)		•
Intubation in the ER (Yes or No)		•
Need for NIV ventilation		•
Number of total albuterol treatment during the ER stay		•
Total accumulative dose of albuterol during the ER stay		•
Number of total ipratropium treatment during the ER stay		•
Total accumulative dose of ipratropium during the ER stay		•
Total dose of steroid (prednisone equivalent in mg)		•

Table 1

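### The 180-minute reading is waived after early ER discharge, and the plan names no analysis that is sure to keep those patients, so the 180-minute airflow difference may be partly understated

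*Combined protocol and SAP*

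**What the plan says.** Section III.E.3.2 drops the 180-minute data collection for any patient "discharged from the ER within 3 hours from the initial bronchodilator therapy then the data collection at 3 hours mark will be waived". It does not define discharge, although the recorded dispositions are home, floor or ICU.

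Section III.B names the analysis: "ANCOVAs with adjustment for baseline values, and incorporating repeated measures where appropriate, will be utilized for the following secondary outcomes". Six of the listed outcomes have a 180-minute comparison: PEFR % predicted, FEV1 % predicted, absolute FEV1, Borg score, accessory muscle score and heart rate. The two clinical scores, for example, are listed as "Borg dyspnea score at 30 minutes, 60 minutes and 180 minutes, accessory muscle use score at 30 minutes, 60 minutes and 180 minutes". The section gives no model type, covariance structure, missing-data rule or sensitivity analysis. The analysis set is defined as "using the data collected from all randomized participants who completed the study procedures", with signature of both consent parts also required. Of the plot it says: "The outcomes which are measured at different time points will be averaged for each group and plotted to visualize the trajectory of those outcomes".

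A further reading is due when the patient leaves. The Subject Timeline calls for data "at 180 ± 10 minutes and upon disposition from the ER", and section 3.2 repeats this as "180±10 minutes and at the disposition from the ER". The disposition block of Table 1 and section 3.3 list no airflow, dyspnea or vital-sign reading at that point, and no analysis uses one.

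The Rationale (II.B) and the Outcomes section both expect better airflow to bring a shorter ER stay.

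**The concern.** On the trial's own hypothesis, whether a patient has a 180-minute value depends on how well that patient responded. A patient who recovers quickly may leave before three hours. If the new device works, more such patients are in its arm. Those who remain for the 180-minute reading are then the slower responders, and the selection is heavier in the Aeroneb arm.

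An ANCOVA on the observed values, or a plot of observed averages, would show a smaller difference than exists. A lasting benefit could look as if it fades after the first hour.

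**Working it through.** **The plan's own figure.** Section III.B uses a difference of 10 points, SD 14.4, two-sided alpha 0.05 and an equal-variance t-test. Exact power is 79.3% with 33 per group and 80.5% with 34, so the stated 34 reproduces. It concerns the 30-minute outcome, which the waiver does not touch.

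**Inputs for 180 minutes.** From the plan: SD 14.4, baseline mean 27, control mean 39 at 30 minutes, effect 10. Not in the plan, and so assumed: control means of 45 and 50 at 60 and 180 minutes, an effect of 10 at every later time, a within-patient correlation r of 0.5 or 0.7, and 10% to 50% of controls leaving early under one threshold common to both arms.

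**The mechanism by hand (raw averages, as in the plot).** If patients above a 60-minute threshold leave, the mean 180-minute value of those who stay falls by r × SD × φ(z)/Φ(z), where z is the standardised threshold. Let 30% of controls leave:

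- Control: z = 0.524; φ/Φ = 0.348/0.700 = 0.497.
- Aeroneb: z = 0.524 − 10/14.4 = −0.170; φ/Φ = 0.393/0.432 = 0.909. The share leaving is 1 − 0.432 = 57%.
- Raw difference with r = 0.7: 10 − 0.7 × 14.4 × (0.909 − 0.497) = 5.8. With r = 0.5 it is 7.0.

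Baseline adjustment recovers part of this loss: simulated ANCOVA for the same case gives 8.3.

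**Simulation, 400,000 patients per scenario, true difference 10.** The model column is a regression prediction of the missing value from arm, baseline, 30 and 60 minutes. It stands in for a likelihood repeated-measures model.

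| What drives early discharge | Observed-only ANCOVA | Model |
|---|---|---|
| 60-minute PEFR | 7.7–9.0 | 9.9–10.1 |
| 60-minute PEFR plus noise | 9.1–9.6 | 10.0–10.1 |
| Later airflow (180-minute value, or its average with the 60-minute value) | 3.7–7.9 | 3.5–8.6 |
| Poor response, or both extremes | 7.0–9.5 | 9.9–10.1 |
| Nothing related to response | 9.9–10.1 | 9.9–10.0 |

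With a true effect of 0 and a common rule (30% leaving on 60-minute PEFR), both estimates are 0.02.

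**A second set of scenarios** varied the time of the discharge decision. It assumed control means of 43 at 60 minutes and 50 at 180, correlations with the 180-minute value of 0.74 at 60 minutes and 0.82 at 120, and a baseline correlation of 0.5. Three recovery curves were used.

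| Assumed rule | Aeroneb waived | Observed-only | Model |
|---|---|---|---|
| Few leave | 4–24% | 8.5–9.4 | 9.4–10.0 |
| Loose link to PEFR | 17–58% | 8.3–9.0 | 9.3–9.7 |
| All above 70% predicted at 120 minutes | 15–23% | 7.8–8.5 | 9.1–9.5 |
| Stricter cuts | 24–64% | 6.3–8.0 | 8.4–10.1 |
| Most severe rule | 50–61% | 5.4–6.0 | 7.7–8.1 |

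The undefined word matters. If discharge also covers early admissions (assumed to be those below 30% at 120 minutes), the third row becomes 6.5–6.7 observed-only and 8.4–8.6 with the model.

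**Unequal rules.** Take a true effect of 0, a control mean of 47 at 120 minutes (assumed), and early discharge above 60 in control but above 70 in Aeroneb. Observed-only ANCOVA gives +1.8. With the cuts reversed it gives −1.9.

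**The case against.** Four objections deserve weight.

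- **The plan does mention repeated measures.** A reader might infer that every planned analysis discards the waived patients. The text does not support that: a likelihood model would keep them through their 30- and 60-minute values and would fit the wording. A complete-case repeated-measures ANCOVA fits it equally well, so what stands is that neither is chosen. Likewise, a patient whose reading is formally waived has most naturally completed the procedures, but the analysis-set sentence does not say so.
- **The size is unknown.** This stands in full. The documents give no three-hour discharge rate, discharge rule, 180-minute mean or correlation. Even with all 34 per arm measured, the standard error is about 14.4 × √(1 − 0.5²) × √(2/34) = 3.0, taking a baseline correlation of 0.5. The mild scenarios lose well under that.
- **The direction is not guaranteed.** A reader might infer that the error can only shrink the difference and so cannot create a false positive. That needs the same discharge rule in both arms. The Study Procedures leave patient, nurse and respiratory therapist unblinded. The treating physician is meant to be blinded, but is asked to stay away during treatment only if possible. The unequal cuts above are hypothetical, but they show that either sign can occur.
- **The remedy is partial.** This also stands. When discharge tracks later airflow, the model's range (3.5–8.6) is close to that of ANCOVA (3.7–7.9), and in one scenario the model was slightly worse (3.5 against 3.8).

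The waiver itself is practical, since a patient who has gone home cannot be measured in the ER. Length of stay and hospitalization remain as separate outcomes, so earlier discharge would still be visible.

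**Conclusion.** The concern holds as under-specification with a foreseeable bias. The plan waives the 180-minute reading for a group that its own hypothesis expects to differ by arm, and it commits to no analysis that is sure to keep them.

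If Aeroneb works and discharge follows response by a common rule, the observed-only 180-minute airflow difference and the plotted means are partly understated. For a true 10 points, observed-only ANCOVA gave about 9.4 down to 5.4 in the second set of scenarios, and as little as 3.7 where discharge tracked airflow after 60 minutes. All of these rest on assumed discharge rules, later means and correlations.

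With equal devices and a common rule there is no bias. With thresholds that differ by arm it can go either way, by about 2 points in the example. The heart-rate direction is not established, because the protocol allows that Aeroneb may deliver more albuterol. The primary outcome, its power and the 68 patients are unaffected.

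**What to change.** 1. In III.B, name as the main 180-minute analysis a likelihood-based repeated-measures model on the 30-, 60- and 180-minute readings, with arm by visit, baseline by visit and unstructured covariance. State that it includes all randomized patients with usable consent, including those whose 180-minute reading was waived. Draw the trajectory plot from this model in place of raw averages.
2. Reconcile Table 1 and section 3.3 with the Subject Timeline and section 3.2, so that the disposition reading and its clock time are captured.
3. State in 3.2 which dispositions count as discharged for the waiver. Report waived readings and disposition location by arm.
4. Give two sensitivity analyses: observed-only ANCOVA, and an analysis that uses the disposition reading.

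The cost is a short paragraph in III.B, a clause in 3.2, a line in 3.3 and 13 rows in Table 1 (the 12 measurements listed at 180 minutes plus the time). Section 3.2 already requires the readings. The analysis work grows a little. The model removes the bias fully only if discharge depends on the recorded 30- and 60-minute values. It can also overshoot: if only discharged patients fall back by 5 points before 180 minutes, it exceeded the truth by up to 1.1 points in the assumed scenarios. That is why the sensitivity analyses and the counts by arm belong beside it.

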3.3 Upon disposition from the ER
The following data will be collected: the disposition location (home, floor or ICU), length of stay in the ER (from ER arrival time to the disposition order placement time), intubation in the ER, need for NIV ventilation, number and total doses of albuterol treatments in the ER and number and total doses of ipratropium in the ER.

F. Assessment of Subject Safety and Development of a Data and Safety Monitoring Plan

1. Definition of Serious Adverse Event (SAE) and Adverse Event (AE) for this study:
For the purposes of this study a SAE is a serious adverse event that is life-threatening or results in death, hospitalization or prolonged hospitalization, significant disability/incapacitation, congenital anomaly or birth defects, or may jeopardize the subject's health and may require medical or surgical intervention to prevent one of the other listed outcomes. A SAE does not necessarily have to have a causal relationship with the study treatment. SAE may not be uncommon in the study due to the acute nature of patients presenting with severe asthma exacerbations that may be enrolled into the study. The study will be conducted in the emergency room, which provides a high level of monitoring and is capable of managing SAE in this acute patient group. It is possible that the Aeroneb group patients may experience more frequent side effects related to potentially more albuterol and ipratropium delivery and those side effects may include arrhythmia and tremor. Those side effects will be monitored closely and patients will be placed on continuous cardiac monitoring during the ER visit to capture any arrhythmia.
2. Reporting timeframe for SAEs and AEs:
SAEs will be reported to the IRB within five business days of the event occurring. The investigators will record and track any SAE or AE that might occur during the study. If a disproportionate number of events occur in either of the groups, then the study will be stopped. A "disproportionate number" is defined as one showing a statistically significant difference in SAEs and AEs occurrence after the recruitment of half the sample size (34 patients).
3. Accountability procedures as they relate to drugs, devices, and data:
The Principal Investigator [name] and the research team member [name] will be accountable for the study and interface with Aerogen, the study sponsor.
4. Data and Safety Monitoring Plan:
We do not anticipate serious complications attributable to the device, but will monitor patients for potential adverse effects such as discomfort or cough. Any serious adverse events that occur during use are more likely due to the underlying disease than the device itself, but will be reported promptly to the IRB by the investigators per the reporting timeframes described above.

The Research team will report to the IRB the process of the informed consent after enrolling 10 patients (if this occurs before the study continuing review).

G. Subject Participation

1. Recruitment:

Patients presenting with severe asthma exacerbation to Tufts Emergency Room will be recruited on to the study. Patients who meet any exclusion criteria will not be screened for possible enrollment. Patients will be approached at their bedside by the PI, co-investigator or research coordinator. No advertisements will be used.

2. Registration:

Patients, that can potentially take part in the study, will be assessed by the PI or the co-investigator for their ability to fulfill the eligibility criteria and meet the exclusion criteria, as listed above.

3. Screening Interview/questionnaire: Not applicable

4. Transportation: Not applicable

5. Informed consent process and timing of obtaining of consent:

The participant must have the full mental capacity to provide the consent. The consenting process will be two steps process, each step will involve face-to-face meeting with one of the study investigators at bedside in the ER room

1-The first part of the consent will cover all the essential elements of the informed consent. Given the acuity of the medical condition, it is anticipated that the total amount of time given to this step of the informed consent will be no longer than 10 minutes. No study related procedures will be conducted until this step of the informed consent is signed off by the subject. Permission will also be obtained from the primary provider for the participation of the patient in the study before a discussion with the patient regarding consent occurs.

The patient will be provided with a copy of the consent form to read and all questions will be answered prior to their signing the first part of the consent. In order to determine the subject's understanding of the study, the subject will be asked to describe his understanding of the study back to the investigator obtaining the consent. The subject will be encouraged to call the investigator with any questions. No study procedures will be performed other than chart review to determine eligibility prior to obtaining informed consent. The investigators recognize the potential vulnerability of the patient in this setting (i.e., being acutely ill) and thus will terminate the consent discussion in any situation where the patient appears to be uncomfortable or apprehensive about providing consent for participation in the study.

2-The second part of the informed consent will take place after the study procedures have been performed and the patient condition has been stabilized. The investigator will meet face-to-face with the subject and review the ICF again with the subject in more detailed manner. The subject will be asked to sign a separate section of the ICF re-consenting that they agreed to participate in the study.

Subjects who do not sign the second part of the ICF will be withdrawn from the study and data collected on those subjects may not be used for the study.

It will be explained that if they refuse to be in the study it will not affect their care or medical treatment outside of the study.

If non-English speaking persons will be enrolled, state the informed consent process for enrolling the subjects, including who will conduct the consent interview, use of interpreters, translated documents, etc.: Only English speaking persons will be enrolled as it will be difficult to communicate with non-English speaking patients about the PEFR maneuvers and the dyspnea scoring. Timely assistance from the interpreter service personnel may not be feasible given the acuity of the cases. Interpreter phone will not be sufficient as it would be hard to demonstrate the maneuver through phone interpretation.

6. Location where study will be performed:

The study will be performed at the Emergency Room at Tufts Medical Centre. Study records will be kept in a locked filing room.

7. Personnel who will conduct the study, including:

a. Present during study procedure(s) and their proximity during the study:

The PI, co-investigator or the research coordinator will oversee the study procedure. Normal clinical care of patients will be performed by the patient's assigned nurse, respiratory therapist and doctor in the emergency room.

b. Primary responsibility for the following activities:

i. Obtaining informed consent:

The principal investigator and the co-investigators will be responsible for obtaining the informed consent from the patients.

ii. Providing on-going information to the study sponsor and the IRB:

[name] and [name] will be responsible for providing on-going information to the study sponsor and the IRB.

iii. Maintaining participant's research records:

[name] will be responsible for maintaining the participant's research records. The records will be maintained up to 7 years as per the IRB policy.

8. Subject fees:

There will be no fees paid to subjects for the study. It is part of their emergency visit care treatment

9. Study results:

Study results will not be given to patients.

10. Procedures to protect subject confidentiality:

Patient confidentiality will be maintained under normal emergency room procedures which are in compliance with the HIPPA rules.

11. Confidentiality:

a. Certificate of Confidentiality:

Certificate of confidentiality is not relevant for this research study

b. How data will be coded, recorded, and stored to protect confidentiality:

Study participants will be allocated a study number, which will be used as a study identifier on all study forms. The study data and records will be kept locked.

c. Parties who will have access to the date, including the key to the identity code:

The study PI, [name] and research team member [name] will have access to the study data and the identity codes.

d. Parties who will have access to research records:

The study PI, [name] and research team member [name] will have access to the study data.

12. Collaboration:

This is not a collaborative study.

13. Alternatives:

Patients not participating in this study will receive usual ER care as determined by the ER.

14. How new information will be conveyed to the study subject and how it will be documented:

In the event new information is discovered about the study, a letter describing the new information will be mailed to the contact address for each subject who participated in the study.

15. Payment, including a prorated plan for payment:

There will be no payment for participants. The study is part of Emergency Room care that a patient is receiving as part of their visit.

16. Payment for a research-related injury:

Aerogen (the study sponsor) agrees to reimburse the site for the costs of the care and treatment of any illness or injury to a subject directly resulting from his or her participation in the Study; provided, however, that such illness or injury is not a result of the negligence or misconduct of Site, Principal Investigator or any of Site's employees.

I. Outcomes:

The expected outcome of the study is that the Aeroneb system arm will have higher PEFR after treatment with bronchodilator as compared with the small volume jet nebulizer arm. It is also expected that the improvement in the PEFR in the Aeroneb arm will translate in improvement in the respiratory outcomes like dyspnea, accessory muscle use, length of ER stay and need for hospitalization.

Primary outcome: the mean of PEFR percentage of predicted at 30 minutes after the initial bronchodilator treatment in the Aeroneb group will be 10 points higher than the mean of PEFR percentage of predicted at 30 minutes after the initial bronchodilator treatment in the small volume jet nebulizer group.

Secondary outcomes:

- Change in the absolute value of PEFR (L/minute) at 30 minutes after the initial bronchodilator treatment in the Aeroneb group compared to the small volume jet nebulizer group
- Change in the PEFR percentage of predicted at 60 minutes and 180 minutes after the initial bronchodilator treatment in the Aeroneb group compared to the small volume jet nebulizer group
- Change in the FEV1 percentage of predicted at 30 minutes, 60 minutes and 180 minutes after the initial bronchodilator treatment in the Aeroneb group compared to the small volume jet nebulizer group
- Change in the absolute FEV1 (L/Second) at 30 minutes, 60 minutes and 180 minutes after the initial bronchodilator treatment in the Aeroneb group compared to the small volume jet nebulizer group
- The Borg dyspnea score at 30 minutes, 60 minutes and 180 minutes after the initial bronchodilator treatment in the Aeroneb group compared to the small volume jet nebulizer group
- The accessory muscle use score at 30 minutes, 60 minutes and 180 minutes after the initial bronchodilator treatment in the Aeroneb group compared to the small volume jet nebulizer group

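### As worded, the safety stop at 34 patients can be met by fewer hospital admissions on Aeroneb, which the plan elsewhere counts as a benefit

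*Combined protocol and SAP*

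**What the plan says.** Section III.F.1 counts as an SAE an event that is "life-threatening or results in death, hospitalization or prolonged hospitalization, significant disability/incapacitation", among other criteria. It adds: "A SAE does not necessarily have to have a causal relationship with the study treatment". It also warns that "SAE may not be uncommon in the study due to the acute nature of patients presenting with severe asthma exacerbations". It does not exempt admission for the attack that brought the patient to the ER.

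Section III.F.2 sets the stopping rule: "If a disproportionate number of events occur in either of the groups, then the study will be stopped". The threshold for stopping follows in the next sentence of that section; it "is defined as one showing a statistically significant difference in SAEs and AEs occurrence after the recruitment of half the sample size (34 patients"). The rule names no test, alpha or counting unit, and does not say whether SAEs and AEs are pooled. Section III.B makes all testing two-sided at 0.05.

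Elsewhere admission is an efficacy measure. The Rationale (II.B) and Outcomes (III.I) sections both expect less hospitalization with Aeroneb. The proportion admitted is a secondary outcome, to be compared by chi-square under III.B.

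On direction of risk, III.D.1 says of respiratory failure that "it is unknown if the risk of such complications is higher in any arm". It also says that "the Aeroneb group patient may experience more frequent side effects related to potentially more albuterol and ipratropium delivery".

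**The concern.** The same event, admission from the ER, appears to serve two opposed purposes. As a secondary outcome, fewer admissions on Aeroneb would be a success. As an SAE under a rule with no direction, the same difference, if significant at 34 patients, would oblige the investigators to stop. The rule leaves no stated room for judgement, so a result in the hoped-for direction could end the trial at half its planned size, with the primary comparison under-powered.

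**Working it through.** **1. The plan's own figure.** With a difference of 10, SD 14.4 and 34 per group, the noncentrality is 10 / (14.4 × √(2/34)) = 2.86. The exact two-sided t-test power is 0.805 (0.793 at 33 per group), so the planned 34 per group is right, and half of 68 is the 34 patients in the rule. With 17 per arm the noncentrality is 10 / (14.4 × √(2/17)) = 2.02 and power is about 50%. That is what a stop at the look would leave.

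**2. Arms at the look.** Randomization is 1:1 in blocks of 6. Since 34 = 5 × 6 + 4, the split is 15 + 15 plus four patients from a sixth block: 17/17, or 16/18 at the extreme.

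**3. How few admissions are enough (17 vs 17, jet vs Aeroneb).**
- Uncorrected chi-square, 4 vs 0: 34 × (4 × 17)² / (17 × 17 × 4 × 30) = 4.53, p = 0.033.
- Fisher, 5 vs 0: 2 × C(17,5) / C(34,5) = 2 × 6188 / 278256, p = 0.044.
- Also significant: 6 vs 1 by chi-square (p = 0.034) and 7 vs 1 by Fisher (p = 0.039).

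**4. Chance of a stop because Aeroneb has fewer events.** Sum Bin(x; 17, p_jet) × Bin(y; 17, p_Aeroneb) over all pairs with y < x and p < 0.05. The jet rates of 20% and 33% are the one-fifth to one-third in section I, which describes ED patients generally. The Aeroneb rates are assumed. The range runs from Fisher to uncorrected chi-square.

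SAEs tested alone and made up of admissions:

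| Jet vs Aeroneb | Chance of stop |
|---|---|
| 33% vs 20% | 6.8-12.3% |
| 20% vs 10% | 5.3-11.2% |
| 33% vs 16.5% | 10.8-18.3% |
| 33% in both | 1.0-2.4% |

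SAEs and AEs pooled as patients with any event, with AEs independent of admission: pooled rate = 1 − (1 − admission) × (1 − AE). AE rates are assumed.

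| Admissions, jet vs Aeroneb | AEs, jet vs Aeroneb | Pooled rates | Chance of stop |
|---|---|---|---|
| 33% vs 20% | 20% vs 20% | 46.4% vs 36.0% | 4.8-9.5% |
| 33% vs 20% | 10% vs 20% | 39.7% vs 36.0% | 1.9-4.2% |
| 33% vs 20% | 10% vs 30% | 39.7% vs 44.0% | 0.6-1.5% |
| 20% vs 10% | 20% vs 20% | 36.0% vs 28.0% | 3.3-6.8% |
| 20% vs 10% | 10% vs 20% | 28.0% vs 28.0% | 1.0-2.3% |
| 20% vs 10% | 10% vs 30% | 28.0% vs 37.0% | 0.2-0.6% |

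**5. Sensitivity.** With arms of 16 and 18, the first three rows of the SAE-only table become 9-15%, 7-13% and 14-22%. Admissions of 50% vs 25%, both assumed for a sicker population, give 21-33% tested alone and 3-23% pooled over the same three AE cases. All figures take one look at 34. If the rule applies repeatedly from then on, the chances rise.

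**6. The other direction.** If admissions were 33% jet vs 53% Aeroneb (assumed), a test of admissions would stop the trial for the Aeroneb excess with probability 14-23%.

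**The case against.** The best counter-argument concerns what an adverse event is. Hospitalization makes an event serious, but an adverse event must come first, and here the attack precedes enrolment and is the reason for entry. Dropping the causality requirement removes an attribution test; it does not turn the presenting illness into an adverse event. Disposition is also collected and analysed separately. Section III.F.4 says "Any serious adverse events that occur during use are more likely due to the underlying disease than the device itself", but that sentence covers events while the device is in use and fits an admission decision poorly. The expectation that SAEs will not be rare is followed by a remark on the ER's ability to manage them, which suits arrhythmia or respiratory failure better than admission.

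This stands as a possible reading. No sentence adopts it, and the definition taken literally includes hospitalization with no exemption, so the plain wording leaves the conflict open.

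The second counter-argument also has force: the rule names SAEs and AEs together, so the SAE-only figures may not describe it. Pooling lowers the chance, and if Aeroneb has more side effects, as III.D.1 allows, the chance can fall to the level expected with no difference, or below. With expected counts under 5 per arm, the Fisher end of each range is also the safer one.

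A reader might infer that the trial is likely to be stopped for benefit, or that the whole rule should look only for harm on Aeroneb. The documents support neither. The larger probabilities need admission rates that the plan does not give, and III.D.1 leaves open which arm carries more risk of respiratory failure, which is a basis for a two-directional rule on other events.

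**Conclusion.** The point holds for admissions only. Followed as written, III.F.1 and III.F.2 let fewer Aeroneb admissions meet a mandatory safety stop, while the Rationale and Outcomes sections treat the same difference as a benefit. This is a conflict between sections and not merely missing detail. It rests on the plain wording of the SAE definition; the documents do not show that the sponsor meant to count these admissions.

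The chance is modest: at most about 10% in the pooled cases at the plan's own background admission rates, and about 5-18% if SAEs are tested alone. The consequence would be loss of half the sample. It should be corrected, because the correction is a matter of wording.

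**What to change.** Reconcile III.F.1 and III.F.2 with the secondary outcome so that fewer Aeroneb admissions cannot stop the trial. Either wording would do:

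- **(i)** Leave admission for the presenting exacerbation out of the stopping comparison, still report it to the IRB, and analyse it by arm as the secondary outcome. If the narrower reading was intended, this simply writes it down.
- **(ii)** Compare these admissions separately, and let them count toward a stop only when the excess is on Aeroneb. A two-sided 0.05 test acted on in one direction leaves III.B unchanged.

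Under either, state that a patient who also has another SAE, such as respiratory failure, still counts for that event in the two-directional comparison. Otherwise the exclusion could remove events that the rule is meant to catch.

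No extra data are needed. Option (i) means that an Aeroneb excess of such admissions no longer triggers a stop. That gives up the 14-23% chance in step 6, which is no smaller than the unwanted chance in most of the cases above. Admissions reported as SAEs would still reach the IRB within five business days. Option (ii) keeps that trigger, but a jet-arm excess of admissions no longer stops the trial, and one more comparison is needed.

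Naming the test, the counting unit and whether SAEs and AEs are pooled would be useful in the same edit, but the point does not depend on it.
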